#### 9.2.3. Exploratory Endpoints

- Change from Baseline in PGA-F at Week 16.
- Change in ss-IGA from Baseline at Week 16 in the subgroup of patients with Baseline score of at least 2 (mild scalp psoriasis).
- Change from Baseline of scalp itch NRS at Week 16 in the subgroup of patients with a Baseline score of at least 4 on the 11-point NRS.

This document is confidential.

- [REDACTED]  
[REDACTED]
- Change in cardiovascular risk factors at Week 16. The following parameters will be collected: weight, BMI, waist and hip circumferences, blood pressure, fasting serum glucose, triglycerides, cholesterol (total and HDL/LDL fractions), and C-reactive protein.

The cardiovascular risk factors that will be collected are as follows: weight, body mass index, waist and hip circumferences, blood pressure, fasting serum glucose, triglycerides, cholesterol (total and HDL/LDL fractions), and C-reactive protein.

All exploratory endpoints will be summarized descriptively in the ITT Population.

PGA-F, ss-IGA, scalp itch NRS, [REDACTED], and cardiovascular risk factors (including change from baseline values) will be listed.

This document is confidential.

[figure not shown]
## 10. Pharmacokinetics

Exploratory endpoint: Plasma levels of the drug and its metabolites at scheduled visits.

Blood samples will be collected for measurement of concentrations of orismilast and its major metabolites (LEO 40815 and LEO 32728) as specified in the SoA in Protocol Section 10 before the morning dose of the study drug. The concentration of study drug will be determined from the plasma samples using a validated analytical method.

Blood sampling for measuring trough levels: The patients will be instructed to self-administer the study drug approximately [redacted] hours prior to the planned blood collection for PK analysis. The date and time of the dose taken prior to the PK blood sampling will be collected and registered. It is recommended to have date and time of last subject's drug intake before PK sampling recorded in subject's source and in the eCRF as well.

Blood sampling for calculation of PK profiles: In addition to the sample collected for measuring trough levels, patients will be offered optional participation in specific blood sampling for calculation of PK profiles. This additional procedure is voluntary for patients and patient's consent will be obtained before collection of the blood samples. For PK profiling, [redacted] additional blood samples will be collected during each visit at [redacted] and [redacted]. The patient will be instructed to take the next dose of the study drug in the clinic and blood samples will be taken at the following timepoints: [redacted] (estimated Cmax), [redacted] after intake of the study drug, as shown in the figure below. An additional [redacted] blood sample will be collected if the patient accepts. The actual date and time of the study drug administration in the clinic and each blood sample collection will be recorded.

Abbreviations: Lab, laboratory; PK, pharmacokinetics

The plasma levels of the drug and its metabolites will be summarized descriptively by visit and hour.

A listing of PK levels will be presented by treatment group, subject number, and collection date and time.

This document is confidential.

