8.4. Study Withdrawal, Removal, and Replacement of Patients

If a patient discontinues study treatment and is withdrawn from the study for any reason, the study site must immediately notify the medical monitor. The date and the reason for study discontinuation must be recorded on the electronic case report form (eCRF). Patients who complete or discontinue early from the study will be asked to return to the study site within 4 weeks of the last administration of study drug to complete EOT assessments as indicated in the

Schedule of Assessments (Table 4). If the study treatment is permanently discontinued, the patient will remain in the study to be evaluated for safety.

In the event that a patient discontinues prematurely from the study because of a TEAE or serious TEAE assessed as \geq Grade 3 (\geq Grade 2 for the system organ class [SOC] of cardiac disorders) according to Common Terminology Criteria for Adverse Events version 5 (CTCAE v 5), the TEAE or serious TEAE will be followed up until it resolves (returns to normal or Baseline values) or stabilizes, or until it is judged by the Investigator to no longer be clinically significant.

Once a patient is withdrawn from the study, the patient cannot reenter the study.

A patient may voluntarily withdraw or be withdrawn from the study at any time for reasons including, but not limited to, the following:

- unacceptable toxicity or AE
- patient's withdrawal of consent: at any time, a patient's participation in the study may be terminated at his/her request or on the basis of the Investigator's clinical judgment. The reason for patient withdrawal will be noted on the eCRF.
- intercurrent illness: a condition, injury, or disease unrelated to the primary diagnosis that became apparent during treatment and necessitated the patient's termination from the study
- general or specific changes in the patient's condition that renders him/her ineligible for further treatment according to the inclusion/exclusion criteria
- patient fails to adhere to the protocol requirements (eg, drug noncompliance, failure to return for defined number of visits)
- lost to Follow up: the patient stopped coming for visits, and study personnel were unable to contact the patient
- pregnancy, as indicated in Section 12.9.6.

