10. STUDY PROCEDURES

Table 4 outlines the timing of procedures and assessments to be performed throughout the study. Section 12.5 specifies laboratory assessment samples to be obtained. See Sections 11 and 12 for additional details regarding efficacy assessments and safety assessments, respectively.

 Table 4.
 Schedule of Assessments

	Screening		Follow up						
Procedure	Between Day -28 and -1	Day 1 (Baseline)	W1 (±1d)	W2 (±1d)	W4 (±2d)	W8 (±3d)	W12 (±3d)	W16 (EOT/ET; ±3d)	W20 (±3d)
Informed consent (before any study procedures)	X								
Demography	X								
Medical history, including medication, alcohol, and smoking history (last 6 months)	X								
Concurrent medication review	X	X	X	X	X	X	X	X	X
Inclusion and exclusion criteria	X	X							
Physical examination ^a	X	X						X	X
12-lead ECG (single measurement)	X				X	X		X	
Vital signs ^b	X	X			X	X	X	X	X
Weight ^c	X	X			X	X	X	X	X
Height ^c		X							
BMI ^c		X				X		X	X
Waist and hip circumferences ^c		X				X		X	X
Randomization		X							
Adverse events	X	X	X	X	X	X	X	X	X
Blood sample for serology (HIV antibody, HBV, HCV, HBsAg, HBcAb, and HBsAb)	X								
Safety laboratory assessments (hematology, serum chemistry, urinalysis)	X	X			X	X		X	
Cardiovascular risk factor laboratory assessments ^{c,d}		X						X	
Pregnancy test ^c	X	X			X	X	X	X	
Blood samples for drug and metabolite PK analysis: trough levels (before study drug administration)		X			X	X		X	
Blood samples for drug PK profile (optional)					X			X	
		X						X	

	Screening		Follow up						
Procedure	Between Day -28 and -1	Day 1 (Baseline)	W1 (±1d)	W2 (±1d)	W4 (±2d)	W8 (±3d)	W12 (±3d)	W16 (EOT/ET; ±3d)	W20 (±3d)
IGA, BSA, and PASI	X	X			X	X	X	X	X
PGA-F		X						X	X
Scalp Psoriasis ss-IGA		X						X	X
Scalp itch NRS		X						X	
		X						X	X
PSS		X			X	X	X	X	X
C-SSRS	X	X			X	X	X	X	X
DLQI		X						X	X
HADS		X			X	X	X	X	X
Dispense study drug		X	Xh	Xh	X	X	X		
Collect study drug including packaging			Xh	Xh	X	X	X	X	
Compliance check			X	X	X	X	X	X	

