13.1.1. Blood Samples

Blood samples of approximately mL will be collected for measurement of concentrations of orismilast and its major metabolite (LEO 40815) as specified in the Schedule of Assessments (Table 4) before dose of the study drug. The actual date and time of each blood sample collection will be recorded.

Blood sampling for measuring trough levels: The blood collection for PK analysis should preferably be conducted approximately hours after the last study drug administration. It is recommended to have date and time of patient's last drug intake before PK sampling recorded in patient's source and in the eCRF as well.

Blood sampling for calculation of PK profiles: In addition to the sample collected for measuring trough levels, patients will be offered optional participation in specific blood sampling for calculation of PK profiles. This additional procedure is voluntary for patients and patient's consent will be obtained before collection of the blood samples. For PK profiling, additional blood samples will be collected during each visit at and and and are the patient will be instructed to take the next dose of the study drug in the clinic and blood samples will be taken at the following timepoints: (estimated C_{max}), after intake of the study drug, as shown in Figure 2. An additional optional blood sample will be collected if possible for the patient. The actual date and time of the study drug administration in the clinic and each blood sample collection will be recorded.

Figure 2 Pharmacokinetic Blood Sample Collection

Abbreviations: Lab, laboratory; PK, pharmacokinetics

Details of PK blood sample collection, processing, storage, and shipping procedures are provided in a separate laboratory manual.

UNION therapeutics A/S
Orismilast
UNI50001-203
Version 3.0

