### 7.4. Visit Windows

If there are multiple planned assessments for any study procedure at a given time point, the latest non-missing value will be used for summarization. Unscheduled assessments will be listed and will be used to flag baseline visit if this is the last non-missing assessment before the first dose of study drug, but unscheduled assessments will not be included in the summarization, unless to be used to avoid missing data at Week 4, 8, 12, 16 and 20.

Visits in RAVE captured as 'Week 16 / EoT and 'Week 20 / Follow-up' will be reassigned to either 'Week 16' or another scheduled post-baseline visit or 'EoT' and 'Week 20' or 'Follow-up' as follows: If a patient completed the study treatment (based on the End-of-Treatment form information), data captured in RAVE as 'Week 16 / EoT', will be presented as 'Week 16' irrespectively of violation of visit window. If a patient discontinued the study treatment, provided that no data are available from a certain scheduled post-baseline visit (Week 4, 8, 12, 16) for a subject, data captured on the 'Week 16 / EoT' visit have the potential to be assigned to a particular scheduled visit in data summaries and analyses, provided the data are collected between 13 days before and 14 days after the planned time point for the scheduled visit, as displayed in table below:

This document is confidential.

Visit (target day)	Visit window (day is date of assessment minus date of first dose)
Week 4 (day 28)	Day 15 to 42
Week 8 (day 56)	Day 43 to 70
Week 12 (day 84)	Day 71 to 98
Week 16 (day 112)	Day 99 to Day 139 *

\* Week 16 uses a broader visit window.

If the 'Week16/EoT' visit falls outside the visit schedule in the trial procedure it will be present as 'EoT'.

If the subject completed study treatment, data captured in RAVE as 'Week 20 / Follow-up' will be presented as 'Week 20' irrespectively of violation of visit window. If the subject did not complete study treatment, data captured in RAVE as 'Week 20 / Follow-up' will be presented as 'Follow-up'.

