14.2.3		Exploratory Parameters	
	14.2.3.1	Change from Baseline in Physician's Global Assessment of Finger Nails (PGA-F) at Week 16 Exploratory Analysis: Descriptive Statistics	ITT Population
	14.2.3.2	Change in Scalp-Specific Investigator Global Assessment (ss-IGA) from Baseline at Week 16 Exploratory Analysis: Descriptive Statistics	ITT Population - Patients with Baseline Score of at least 2 (Mild Scalp Psoriasis)
	14.2.3.3	Change from Baseline of Scalp Itch Numeric Rating Scale (NRS) at Week 16 Exploratory Analysis: Descriptive Statistics	ITT Population - Patients with Baseline Score of at least 4 on the 11-point NRS
	14.2.3.4	[REDACTED] [REDACTED] Exploratory Analysis: Descriptive Statistics	ITT Population - [REDACTED] [REDACTED] [REDACTED] [REDACTED] [REDACTED]
	14.2.3.5	Change in Cardiovascular Risk Factors at Week 16 Exploratory Analysis: Descriptive Statistics	ITT Population

This document is confidential.

Header	Table Number	Name	Analysis Population
	14.2.3.6.1	Trough Levels of Orismilast and Metabolites Exploratory Analysis: Descriptive Statistics	ITT Population
	14.2.3.6.2	Plasma Levels of Orismilast and Metabolites Exploratory Analysis: Descriptive Statistics	ITT Population - Patients Having Accepted The Additional Profiles
	14.2.3.6.3	Trough Levels of Orismilast and Metabolites by Time Since Previous Dose Exploratory Analysis: Descriptive Statistics	ITT Population
	14.2.3.7	[REDACTED] [REDACTED] Exploratory Analysis: Descriptive Statistics	ITT Population
14.3		Safety Data	
14.3.1		Displays of Adverse Events	
	14.3.1.1	Overall Summary of Treatment Emergent Adverse Events (TEAEs)	Safety Population
	14.3.1.2	Treatment Emergent Adverse Events (TEAEs) by System Organ Class and Preferred Term Safety Population	Safety Population
	14.3.1.3	Treatment Emergent Adverse Events (TEAEs) by System Organ Class, Preferred Term and Maximum Toxicity Grade	Safety Population
	14.3.1.4	Treatment Emergent Adverse Events (TEAEs) by System Organ Class, Preferred Term and Toxicity Grade	Safety Population
	14.3.1.5	Treatment Emergent Adverse Events (TEAEs) by System Organ Class, Preferred Term and Maximum Relationship	Safety Population
	14.3.1.6	Treatment Emergent Adverse Events (TEAEs) by System Organ Class, Preferred Term and Relationship	Safety Population
	14.3.1.7	Treatment Emergent Serious Adverse Events (TESAEs) by System Organ Class and Preferred Term	Safety Population

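### SAP 7.4 can relabel an early-termination PK sample taken off drug as a scheduled-visit trough, because PK is not exempt from reassignment and Table 14.2.3.6.1 has no stated time-since-dose condition.

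*SAP*

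**What the plan says.** - **Sampling.** The schedule in Protocol section 10 (Table 4) has a row headed "Blood samples for drug and metabolite PK analysis: trough levels (before study drug administration"). It is marked at Day 1, Weeks 4 and 8, and the Week 16 column that doubles as the end-of-treatment and early-termination visit. It is not marked at Week 12.
- **Timing of the early-termination visit.** Under Protocol 8.4, patients who complete or stop early "will be asked to return to the study site within 4 weeks of the last administration of study drug to complete EOT assessments".
- **Relabelling.** Under SAP 7.4, if a patient stopped treatment, data captured as 'Week 16 / EoT' "have the potential to be assigned to a particular scheduled visit in data summaries and analyses". Two conditions apply: the scheduled visit has no data, and the date lies in its window (Day 15 to 42, 43 to 70, 71 to 98 and 99 to 139 for Weeks 4, 8, 12 and 16). Data that do not fit stay under 'EoT'. PK is not mentioned.
- **Summary.** SAP section 10: "The plasma levels of the drug and its metabolites will be summarized descriptively by visit and hour". The index in SAP section 18 lists Table 14.2.3.6.1, "Trough Levels of Orismilast and Metabolites Exploratory Analysis: Descriptive Statistics", for the ITT population with no condition on dosing status. It also lists Table 14.2.3.6.3, "Trough Levels of Orismilast and Metabolites by Time Since Previous Dose Exploratory Analysis: Descriptive Statistics".
- **Last-dose time.** SAP section 10: "The date and time of the dose taken prior to the PK blood sampling will be collected and registered". Protocol 13.1.1 is softer: "It is recommended to have date and time of patient's last drug intake before PK sampling recorded". SAP section 10 repeats that softer sentence as well.

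**The concern.** A trough describes exposure at the end of a dosing interval in a patient who is taking the drug. The reassignment rule suits PASI, where an early-termination value still says something about the patient's disease near that visit. For a drug with a half-life of a few hours it does not suit concentrations: a sample taken days or weeks after stopping says nothing about the assigned dose.

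At stake is how the by-visit trough table reads. The secondary objective is dose response and the choice of a Phase 3 dose, and the stated main purpose of Protocol Amendment 2 was to obtain meaningful PK data. If off-drug samples are commoner in one arm than another, the ratio of mean troughs between doses is distorted, and a reader could mistake that for non-proportional exposure.

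**Working it through.** The plan states no PK figure to reproduce. Its one design figure, 80% power with 50 per arm, does reproduce: the noncentrality is 18.7 / (33 × √(2/50)) = 2.83 and, with 98 degrees of freedom, power is 80.1%. Nothing below uses it.

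**Step 1: can the rule produce the problem?** Suppose the last dose is on Day 12 and the early-termination visit on Day 30, with no Week 4 data. The visit is within 4 weeks of the last dose (30 − 12 = 18 days) and Day 30 lies in the Week 4 window, so the sample may be labelled Week 4. The Week 16 window runs to Day 139, which is 27 days past its target of Day 112. A visit in the Week 12 window would create a Week 12 trough row where none is scheduled, made up of discontinued patients apart from any unscheduled samples.

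**Step 2: what is left in such a sample?** The half-life is 6.48 h for the modified-release tablet (Protocol 5.4.1); estimates for the capsule run from 4 to 10 h (Protocol 5.2.2.1). The planned trough time is redacted, so 12 h is assumed from the twice-daily schedule. The level at t hours relative to a 12 h trough is 2^(−(t − 12)/half-life).

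| Time since last dose | 6.48 h | 4 h | 10 h |
|---|---|---|---|
| 24 h | 28% | 13% | 44% |
| 48 h | 2.1% | 0.2% | 8.2% |
| 72 h | 0.16% | 0.003% | 1.6% |

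Four weeks is 672 / 6.48 = 104 half-lives.

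**Step 3: how far does the mean move?** If a share f of the samples at a visit is off drug with residual r, the reported mean is 1 − f(1 − r) of the on-treatment mean. With r near zero it falls by f.

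**Step 4: how large might f be?** The documents give no discontinuation rates for this trial, so these are assumptions. Discontinuation is 10% in the 20 mg arm and 30% in the 40 mg arm. The last dose is either uniform over Days 1 to 111 or front-loaded (exponential, mean 28 days, truncated to the same span). The return lag is uniform over 0 to 28 days. Visits are labelled by the SAP 7.4 windows when the last dose precedes the target day, and a lag above 2 days counts as off drug. The label probabilities come from 400,000 simulated patients.

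Week 16 with uniform timing shows the arithmetic. A discontinuer has probability 0.236 of being labelled Week 16, and 0.228 of being so labelled with a lag above 2 days.
- 30% discontinuation: f = 0.3 × 0.228 / (0.7 + 0.3 × 0.236) = 8.9%.
- 10% discontinuation: f = 0.1 × 0.228 / (0.9 + 0.1 × 0.236) = 2.5%.

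**Step 5: the 40:20 ratio.** Protocol 5.2.2.1 describes exposure as approximately dose proportional, so take a true ratio of 2.0. The reported ratio is 2 × (1 − f40) / (1 − f20).

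| Visit | Timing | f20 | f40 | Reported ratio |
|---|---|---|---|---|
| Week 4 | uniform | 1.8% | 5.4% | 1.93 |
| Week 8 | uniform | 2.1% | 6.8% | 1.90 |
| Week 16 | uniform | 2.5% | 8.9% | 1.87 |
| Week 4 | front-loaded | 4.6% | 14.4% | 1.79 |
| Week 8 | front-loaded | 2.4% | 8.3% | 1.88 |
| Week 16 | front-loaded | 0.4% | 1.4% | 1.98 |

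If patients return within 7 days instead, the ratio lies between 1.89 (Week 4, front-loaded: f = 2.5% and 8.0%) and 1.99 (Week 16, front-loaded: f = 0.1% and 0.5%).

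**The case against.** The strongest reply is that the sponsor has foreseen late samples. Table 14.2.3.6.3 shows troughs by time since previous dose, PK levels are listed with collection date and time, and the optional profiles are dosed in clinic with actual times recorded. SAP 7.1 also asks for median, quartiles and minimum, so a cluster of zeros would show. All of this stands. It makes the late samples visible, but it does not take them out of Table 14.2.3.6.1.

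The reply also has force on size. If values below quantification are set to missing, most of the dilution goes; quantifiable samples at roughly 24 to 48 h would remain. The endpoint is exploratory and descriptive, and Protocol 7.1 names efficacy and safety outcomes as the basis for dose selection.

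Some stronger readings are tempting, and the documents do not support them:
- **That the trough table takes every sample at a visit.** This would be inferred from silence. Reassignment has two conditions, some early-termination samples stay under 'EoT', and the table shells are a separate document.
- **That the distortion is severe.** Off-drug shares of 10% and 30% would give 2 × 0.70 / 0.90 = 1.56, but that treats discontinuation rates as shares of samples. In the simulation even 50% discontinuation gave at most 25% of samples off drug. The 50% of patients with AEs leading to withdrawal in the Phase 2a trial were on the immediate-release tablet.
- **That the bias must grow with dose.** It depends on when patients stop and how soon they return, as well as on how many stop.
- **That dosing pauses add much.** Under Protocol 9.3.1 the evening dose is taken on the second and third days, so only the second morning is about 24 h after a dose.
- **That grouping by randomised arm misplaces concentrations.** The ITT and safety populations contain the same patients and differ only if someone is mis-dosed, which nothing in the documents suggests.

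**Conclusion.** The concern holds as a flaw in a stated rule. SAP 7.4 applies to data summaries generally and does not exempt PK, so it can label a sample taken days or weeks after stopping as a Week 4, 8, 12 or 16 trough. Nothing in SAP section 10 or the title of Table 14.2.3.6.1 keeps such a sample out.

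The size is modest and conditional. With 10% versus 30% discontinuation and return spread over 4 weeks, a true 40:20 ratio of 2.0 is reported as about 1.8 to 1.9 at most visits. With prompt return it is closer to 2.0. Reaching about 1.58 (2 × 0.753 / 0.954) takes 10% versus 50% discontinuation, front-loaded, at Week 4. All of this assumes that very low values count as zero or near zero, a 12 h trough, and similar timing of discontinuation across arms. The available SAP text gives no below-quantification rule; its programming section is not shown, so a rule may exist there. No hypothesis test or efficacy claim is affected.

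**What to change.** 1. **SAP 7.4:** exempt PK concentrations from the reassignment of 'Week 16 / EoT' data for patients who stopped study drug, and show those samples as 'EoT'.
2. **SAP section 10 and Table 14.2.3.6.1:** include only samples whose recorded time since last dose lies in a prespecified window around the planned trough time. Keep the rest in the listing and in Table 14.2.3.6.3.
3. **SAP section 10:** state how values below quantification enter the summaries.
4. **Last-dose time:** reconcile the two wordings, one saying it will be collected and the other only recommending it, since item 2 relies on this field.

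The cost is a few sentences in the SAP. Table 14.2.3.6.3 shows that the variable needed is already planned. The by-visit trough table will contain slightly fewer samples.

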## **11. Pharmacodynamics**

This document is confidential.

## 12. Safety

All safety analyses will be conducted using the safety population.

Safety will be assessed based on adverse event (AE) reports, physical examination, vital signs, ECGs, clinical laboratory data, HADS and C-SSRS using descriptive statistics.

No inferential statistical analyses are planned on the safety parameters of this study.

